2. SYNOPSIS

Name of Sponsor/Company: Tonix Pharmaceuticals, Inc.	
Name of Investigational Product: TNX-102 SL (Cyclobenzaprine HCl Sublingual Tablets)	
Name of Active Ingredient: Cyclobenzaprine HCl	
Title of Study: A 12-Week Open-Label Extension Study to Evaluate TNX-102 SL Taken Daily at Bedtime in Patients with PTSD	
Studied period (months): 20 Estimated date first patient enrolled: June 2017 Estimated date last patient completed: December 2018	Phase of development: 3
Objectives Primary: The primary objective of the study is to evaluate the safety of TNX-102 SL taken daily at bedtime over an additional 12 weeks in patients with PTSD who have completed a double-blind lead-in study. Secondary: The secondary objective of the study is to evaluate the efficacy of TNX-102 SL taken daily at bedtime over an additional 12 weeks in patients with PTSD who have completed a double-blind lead-in study.	
Methodology: This is an open-label, extension trial designed to evaluate safety over 12 additional weeks of TNX-102 SL therapy taken daily at bedtime for the treatment of PTSD. Patients recruited into this trial are those who have successfully completed a double-blind lead-in study. Patients will not be made aware of the therapy they received during the double-blind study. The study will consist of 5 study visits, including Screening/Baseline Visit 1 (Day 0, which is anticipated to be the same visit as the last visit on double-blind treatment (final primary outcome visit in double-blind lead-in study)), a phone visit after 2 weeks of treatment and in-clinic visits after 4, 8, and 12 weeks of treatment. Eligible patients who provide written informed consent will be provided with two TNX-102 SL 2.8 mg tablets to be taken daily at bedtime for 12 weeks. Patient safety and efficacy parameters recorded at the final primary outcome visit of the double-blind lead-in study will be used as the baseline values for this extension study. Patients will have a telephonic visit at week 2 and then return to the clinic after 4, 8 and 12 weeks of treatment for safety and efficacy assessments. At each clinic visit, patients will return their TNX-102 SL medication and will receive sufficient supplies to last them until the next scheduled visit.	
Number of patients (planned): Completers of the double-blind lead-in study Patients who complete the double-blind lead-in study and satisfy the entry criteria below will be eligible for this study if offered at their enrolling site.	

Inclusion/Exclusion Criteria:**Inclusion criteria:**

1. The patient has completed the final treatment study visit of the lead-in study and is judged by the investigator as reasonably compliant, with at least 60% compliance with study medication usage (based on drug accountability).
2. The patient has provided written informed consent to participate in this extension study.
3. The patient met all prior inclusion and exclusion requirements for the double-blind lead-in study, or the site received medical monitor approval for the patient to remain in the lead-in study after the retrospective discovery of an entry violation that did not pose any threat to the patient's safety or well-being.
4. During the course of the lead-in study, the patient has had no intervening medical conditions including pregnancy, clinically significant increase in suicidal ideation (plan or intent) or significant worsening of depression, newly arising clinically significant abnormal laboratory tests, or any clinically significant, uncontrolled, or unstable medical or surgical condition that could affect the patient's ability to participate in the study or potentially compromise the patient's well-being during the study.
5. The patient does not require treatment with a potent (strong) cytochrome P450 subtype 3A4 (CYP3A4) inhibitor, or St. John's wort.
6. The patient is willing to refrain from use of all other formulations of cyclobenzaprine for the duration of the study.
7. The patient is willing to refrain from use of monoamine oxidase inhibitors for the duration of the study.
8. Female patients of childbearing potential continue to agree to practice one of the medically acceptable methods of birth control detailed in the lead-in study.

Exclusion Criteria:

There are no exclusion criteria for this study.

Investigational product, dosage and mode of administration:

Name: TNX-102 SL (cyclobenzaprine HCl sublingual tablets)

Dose, route, frequency: 2 tablets of 2.8 mg of TNX-102 SL taken simultaneously and sublingually (under the tongue) each day at bedtime starting on Day 0 for 12 weeks.

Duration of treatment:

12 weeks

Reference therapy, dosage and mode of administration: None**Criteria for evaluation:**

The primary objective of the study is to evaluate the safety of treatment with TNX-102 SL 5.6 mg for an additional 12 weeks in patients with PTSD who have completed a double-blind lead-in study. Safety will be assessed by the monitoring and recording of AEs, clinical laboratory tests, vital signs,

the monitoring of suicidality using the Columbia Suicide Rating Scale (C-SSRS) scale and the monitoring of depressive symptoms using the Beck Depression Inventory (BDI-II).

Efficacy will continue to be assessed during 12 weeks of open-label treatment with the Clinician-Administered PTSD Scale for DSM-5 (CAPS-5), the Clinician Global Impression of Improvement (CGI-I), the Sheehan Disability Scale (SDS) and the Patient Reported Outcomes Measurement Information System (PROMIS) sleep disturbance scale.

Statistics

Analysis Population:

The Safety Population will comprise all patients who receive at least 1 dose of study drug.

Treatment Groups:

As an extension of a double-blind study, two treatment groups will be defined as follows:

- TNX-102 SL /TNX-102 SL treatment group: patients who received TNX-102 SL in the double-blind lead-in study and then continued to receive TNX-102 SL in the extension study
- Placebo/TNX-102 SL treatment group: patients who received placebo in the double-blind study and then received TNX-102 SL in the extension study

Patients and site personnel will not be informed concerning treatment assignments in the lead-in study, thus there will be a blinded crossover to active therapy in the extension study.

Baseline:

Baseline will be defined in two different ways as follows: (1) as the last measurement obtained prior to randomization in the double-blind lead-in study (i.e., the original baseline from the lead-in study); and (2) as the measurement obtained at the final primary outcome visit in the double-blind lead-in study and prior to enrollment into the P303 extension study (i.e., the measurement from the final visit of the double-blind lead-in study, which is the same as P303 Visit 1).

Safety Analyses:

Safety data will be summarized by treatment group. Adverse events will be coded using the same version of the Medical Dictionary for Regulatory Activities (MedDRA) as used for the lead-in study and will be summarized overall and by preferred term and system organ class (SOC). Adverse events will also be summarized by severity and relationship to study drug. Serious AEs and AEs leading to discontinuation of study drug will also be summarized. Adverse events that are ongoing at Week 12 from the lead-in study will be transcribed into the eCRF. All other adverse events that are reported after starting TNX-102 SL 5.6 mg in this extension study, or that worsen after entry into the extension study, will be considered newly emergent AEs (NEAEs), even if the type of event was previously reported (and resolved) during the lead-in study.

Actual values and changes from both baselines for clinical laboratory test results, vital sign measurements, and in the BDI-II score will be summarized at endpoint using descriptive statistics (n, mean, SD, median, minimum, and maximum). The number of patients with baseline and treatment-emergent suicidal ideation and/or suicidal behavior or self-injurious behavior, based on the C-SSRS, will be summarized by treatment group.

Efficacy Analyses:

Descriptive statistics by treatment group and study visit will be displayed for a number of efficacy endpoints, including:

- Change from both baselines in the total CAPS-5 score
- Proportion of patients with a CGI-I score of “very much improved” or “much improved” from both baselines
- Change from both baselines in the SDS total score
- Change from both baselines in the individual items assessed using the SDS
- Change from both baselines in patients’ quality of sleep using the PROMIS Sleep Disturbance scale
- Change from both baselines in CAPS-5 symptom cluster subscores
- Proportion of patients with a $\geq 50\%$ improvement from baseline (both baselines) in total CAPS-5 score
- Change from both baselines in BDI-II score

Hypothesis testing will also be performed on the above efficacy endpoints. Missing values will not be imputed, and no adjustments will be made for multiplicity.

IND	Investigational New Drug

Abbreviation or Specialist Term	Explanation
IRB	Institutional Review Board
MCH	Mean corpuscular hemoglobin
MCHC	Mean corpuscular hemoglobin concentration
MCV	Mean corpuscular volume
MedDRA	Medical Dictionary for Regulatory Activities
Mg	Milligram(s)
N, n	Number (of patients)
NA	Not applicable
NEAE	Newly Emergent Adverse Event
PI	Principal Investigator
PO	per os (by mouth)
PROMIS	Patient-Reported Outcome Measurement Information System
PTSD	Post-Traumatic Stress Disorder
RBC	Red blood cell
SAE	Serious Adverse Event
SAP	Statistical Analysis Plan
SD	Standard deviation
SDS	Sheehan Disability Scale
SL	Sublingual
SNRIs	Serotonin–norepinephrine reuptake inhibitors
SOC	System Organ Class
SOP	Standard Operating Procedures
SPI	Safety Planning Intervention
SSRIs	Selective serotonin reuptake inhibitors
TNX-102 SL	Cyclobenzaprine HCl sublingual tablets
US	United States
VA	Veteran's Administration
WBC	White blood count
WHO	World Health Organization

4. INTRODUCTION

The background information provided in the lead-in study protocol and the most current TNX-102 SL Investigator's Brochure is relevant to this extension study. [REDACTED]

[REDACTED]

[REDACTED]

[REDACTED]

[REDACTED]

5. TRIAL OBJECTIVES AND PURPOSE

5.1. Primary Objective

The primary objective of the study is to evaluate the safety of TNX-102 SL taken daily at bedtime over an additional 12 weeks in patients with PTSD who have completed a double-blind lead-in study.

5.2. Secondary Objectives

The secondary objective of the study is to evaluate the efficacy of TNX-102 SL taken daily at bedtime over an additional 12 weeks in patients with PTSD who have completed a double-blind lead-in study.

6. INVESTIGATIONAL PLAN

6.1. Overall Study Design

This is a 12-week, multicenter, open-label extension study designed to accumulate additional safety exposure and efficacy data with daily bedtime dosing of TNX-102 SL 5.6 mg (2 x 2.8mg tablets) in patients with PTSD. This study will be conducted at approximately 35 sites in the United States (US).

Patients who have completed participation in a Phase 3, randomized, double-blind, placebo-controlled study comparing TNX-102 SL 5.6 mg versus placebo for the treatment of PTSD will be eligible. This extension study consists of 5 visits, including the Screening/Baseline visit (which is anticipated to be the same as the primary outcome visit in the double-blind lead-in study), a telephonic visit at week 2, and in-clinic visits after 4, 8 and 12 weeks of treatment (Visits 3-5). The total treatment duration of this study will be 12 weeks. Therefore, the maximum total duration of continuous treatment with TNX-102 SL could be approximately 24 weeks for those patients assigned to active study drug in the lead-in study.

Patient data collected at the Week 12 visit in the lead-in study will be used as one of the defined baselines for this study. There is no need to repeat assessments at Visit 1 for this study, if they were collected in the lead-in study and patients enroll and initiate study treatment within fourteen days of completing the lead-in study.

After the patient has completed his/her participation in the lead-in study and has consented to participate in this open-label extension study, patients will be dispensed a 4-week supply of open-label TNX-102 SL tablets and will be instructed to take the study drug sublingually daily at bedtime, starting on the evening of Visit 1. A phone visit will be completed after 2 weeks of treatment and patients will return to the study center for safety and efficacy assessments at Weeks 4, 8, and 12 (or early termination). At the Weeks 4 and 8 visits patients will return their TNX-102 SL medication and will receive another 4-week supply. Patients will be allowed to take medications deemed appropriate by their health care providers to manage their PTSD and other conditions, including currently approved PTSD therapies. See [Section 8.5](#) for a discussion of allowed concomitant treatments.

The study timeline and events schedule is provided in [Appendix 1](#).

6.2. Number of Patients and Treatment Assignment

The total number of patients enrolled in this study depends on the number of completed patients from the lead-in study who qualify and consent to participate in this open-label extension study.

All patients will be assigned to TNX-102 SL, 5.6 mg regardless of which treatment arm they were randomized to in the lead-in study. No patients or site personnel will know what the prior treatment was in the double-blind lead-in study.

6.3. Study Endpoints

6.3.1. Safety

Safety will be assessed by:

- Adverse events (AE) and serious AEs (SAEs) throughout the entire duration of the study, including assessment of AEs involving the oral cavity
- Changes from both baselines in clinical laboratory test results
- Changes from both baselines indicative of increased suicidal ideation or behavior as assessed by the Columbia Suicide Severity Rating Scale (C-SSRS)
- Change from both baselines in BDI-II
- Changes from both baselines in vital signs and weight

6.3.2. Efficacy

Descriptive statistics by treatment group and study visit will be displayed for a number of efficacy endpoints including:

- Change from both baselines in the total CAPS-5 score
- Proportion of patients with a CGI-I score of “very much improved” or “much improved” from both baselines
- Change from both baselines in the SDS total score
- Change from both baselines in the individual items assessed using the SDS
- Change from both baselines in patients’ quality of sleep using the PROMIS Sleep Disturbance scale
- Change from both baselines in CAPS-5 symptom cluster subscores
- Proportion of patients with a $\geq 50\%$ improvement from baseline (both baselines) in total CAPS-5 score
- Change from both baselines in BDI-II score

Hypothesis testing will also be performed on the above efficacy endpoints. Missing values will not be imputed, and no adjustments will be made for multiplicity.

7. SELECTION AND WITHDRAWAL OF PATIENTS

7.1. Informed Consent

A potential patient may be screened for eligibility only after the nature of the study, its purpose, and any other information relevant to the patient's decision to participate have been explained to him or her and the patient has voluntarily confirmed his or her willingness to participate. The investigator will determine the potential patient's suitability for the study by interviewing the patient and by reviewing the patient's experience in the double-blind lead-in study.

Informed consent is documented by means of a written, signed, and dated informed consent form (ICF). Additional information is provided in [Section 14.3](#).

7.2. Inclusion Criteria

1. The patient has completed the final treatment study visit of the lead-in study and is judged by the investigator as reasonably compliant, with at least 60% compliance with study medication usage (based on drug accountability).
2. The patient has provided written informed consent to participate in this extension study.
3. The patient met all prior inclusion and exclusion requirements for the double-blind lead-in study, or the site received medical monitor approval for the patient to remain in the lead-in study after the retrospective discovery of an entry violation that did not pose any threat to the patient's safety or well-being.
4. During the course of the lead-in study, the patient has had no intervening medical conditions including pregnancy, clinically significant increase in suicidal ideation (plan or intent) or significant worsening of depression, newly arising clinically significant abnormal laboratory tests, or any clinically significant, uncontrolled, or unstable medical or surgical condition that could affect the patient's ability to participate in the study or potentially compromise the patient's well-being during the study.
5. The patient does not require treatment with a potent (strong) cytochrome P450 subtype 3A4 (CYP3A4) inhibitor, or St. John's wort.
6. The patient is willing to refrain from use of all other formulations of cyclobenzaprine for the duration of the study.
7. The patient is willing to refrain from use of monoamine oxidase inhibitors for the duration of the study.
8. Female patients of childbearing potential continue to agree to practice one of the medically acceptable methods of birth control detailed in the lead-in study.

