7.3. Patient Exclusion Criteria

There are no exclusion criteria for this study.

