9.1.2. Screening Overview

The first study visit, Visit 1, will be where the study is explained to the prospective study patient, where written informed consent will be obtained and documented, and where protocol-specified study procedures and assessments will be completed. This visit date is intended to be the same date as the final primary outcome endpoint of the lead-in study (Week 12); however, if there are extenuating circumstances, Visit 1 of P303 may occur within fourteen days of completion of the lead-in study without repeating baseline assessments. If more than fourteen days elapse between the final visit of the lead-in study and start of the P303 study, baseline assessments will need to be repeated.

Once the patient has provided written informed consent to participate and has met all relevant inclusion criteria, this patient is eligible to begin the open-label treatment period starting at bedtime. The patient should be dispensed two bottles of TNX-102 SL tablets, along with instructions on usage. The end-of-study information collected in the double-blind lead-in study will be considered the baseline values for Study P303.

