10.3.1.1. Columbia-Suicide Severity Rating Scale (C-SSRS)

The C-SSRS is a clinician-administered interview developed by researchers at Columbia University to assess suicide risk and to track suicidal ideation and behavior during clinical trials. This scale is intended to be administered by individuals who have received training in its administration. The questions contained in the Columbia-Suicide Severity Rating Scale are suggested probes. Ultimately, the determination of the presence of suicidal ideation or behavior depends on the judgment of the individual administering the scale.

The “since last visit” version of the C-SSRS will be completed at all study visits. Note that if there has been a significant change in responses to this scale indicative of increased suicide risk, appropriate intervention should be prescribed [Section 10.3.1.2](#) and an AE should be recorded.

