10.3.1.2. Safety Planning Intervention (SPI)

The C-SSRS is completed at every visit in order to assess for changes in suicidality during the study. If a patient scores a 4 or 5 on the Suicidal Ideation section of the C-SSRS at a clinic visit following enrollment, the patient should be withdrawn from the study and referred for appropriate emergency care. A score of 4 or 5 should also result in the reporting of a serious adverse event.

If a patient scores a 2 or 3 on the Suicidal Ideation section of the C-SSRS at any visit, the investigator should consider the implementation of a Safety Planning Intervention (SPI). The recommended SPI for this study is the plan developed by [name] and [name] which has been adopted by the U.S. Veteran’s Administration (VA) ([Stanley & Brown, 2012](#)). The VA SPI is a brief clinical intervention aimed at mitigating suicide risk. It consists of a written, prioritized list of coping strategies and sources of support that patients can use to alleviate a suicidal crisis. Sites may use an internally-developed SPI if similar in scope and purpose to the VA SPI.

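### Inclusion criterion 4 ends with the lead-in study, but Visit 1 may come up to 14 days later (or more) and, within 14 days, rely on the lead-in pregnancy test and C-SSRS

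*Protocol*

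**What the plan says.** - **Period covered.** Criterion 4 (Protocol 7.2, repeated in the synopsis) opens: "During the course of the lead-in study, the patient has had no intervening medical conditions including pregnancy, clinically significant increase in suicidal ideation". It goes on to worsening depression, new laboratory abnormalities and unstable illness, all governed by that opening phrase.
- **Timing of entry.** Visit 1 is meant to fall on the day of the final lead-in visit. In extenuating circumstances, however, "Visit 1 of P303 may occur within fourteen days of completion of the lead-in study without repeating baseline assessments" (9.1.2). Beyond fourteen days entry is still possible if the baseline assessments are repeated; no upper limit is given.
- **Eligibility rule.** Once a patient has consented and "has met all relevant inclusion criteria, this patient is eligible to begin the open-label treatment period starting at bedtime" (9.1.2). Section 7.3 adds: "There are no exclusion criteria for this study".
- **Pregnancy test at Visit 1.** Section 9.1.4 has the site confirm the negative result from the final lead-in visit, and Appendix 1 footnote a waives a repeat of anything done there. Section 10.3.1.5 lists the test at Visit 1 without saying that it must be new.
- **C-SSRS at Visit 1.** Section 9.1.4 has the site review the lead-in result, and footnote a again waives a repeat. But 10.3.1.1 says that the since-last-visit "version of the C-SSRS will be completed at all study visits", and 10.3.1.2 says "The C-SSRS is completed at every visit in order to assess for changes in suicidality during the study".

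**The concern.** Section 9.1.2 counts the permitted delay from completion of the lead-in study. By the protocol's own wording, then, the gap lies outside the period that criterion 4 covers. The conditions listed there are the ones the sponsor wants kept out of an open-label study whose primary objective is safety.

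Two separate things are at stake. A condition that is known at Visit 1 but began in the gap is handled by judgement, not by rule. A condition that nobody has noticed, chiefly an early pregnancy, may go unchecked because the waiver lets drug be dispensed on a result up to 14 days old. The C-SSRS adds a practical problem: the protocol gives sites two instructions for a delayed Visit 1.

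**Working it through.** The plan states no figure on this point, so there is none to reproduce. The check is a reading of the entry rules followed by interval arithmetic.

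**Step 1. Does another criterion cover the gap?** Criterion 3 looks back to the lead-in study's own entry requirements. Criteria 5 to 7 concern medicines, and criterion 8 concerns contraception. None names a new condition, although an illness needing a strong CYP3A4 inhibitor would fail criterion 5 through its treatment. With no exclusion criteria, a listed condition arising in the gap fails no written entry criterion. This also holds for gaps above 14 days: repeating the assessments does not change the period that criterion 4 covers.

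**Step 2. What else can act?** At entry, 7.1 requires a suitability interview, 10.1 a review that the patient remains satisfactory for the study, and 9.1.4 a review of new adverse events and medicines. After entry, Table 2 footnote a and 11.4 require withdrawal for pregnancy, and 9.5 allows removal for an illness that puts the patient at risk. The entry checks are discretionary; withdrawal for pregnancy is mandatory but depends on the pregnancy being known.

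**Step 3. Intervals when the lead-in results stand.** Let g be the gap, 1 to 14 days.

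| Check | Next scheduled (Appendix 1) | Days since last check | Range |
|---|---|---|---|
| Urine pregnancy test | Visit 3, Day 28 ± 7 = 21 to 35 | g + 21 to g + 35 | 1 + 21 = 22 to 14 + 35 = 49 |
| C-SSRS, if carried forward | Visit 2, Day 14 ± 3 = 11 to 17 | g + 11 to g + 17 | 1 + 11 = 12 to 14 + 17 = 31 |

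With same-day entry (g = 0) the pregnancy-test interval is 21 to 35 days. If 10.3.1.1 governs, the C-SSRS is done at Visit 1 and its carry-forward interval does not arise.

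**Step 4. Comparison with later visits.** Visits 3 and 4 may already be (56 + 7) − (28 − 7) = 42 days apart. Interval length alone is therefore not the fault. What distinguishes the gap is that it ends with a first open-label dose.

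**Step 5. Doses before the next check.** With one dose each evening from Day 0, 21 to 35 doses precede the Visit 3 pregnancy test. If the C-SSRS was carried forward, 11 to 17 doses precede the Week 2 call. These are the most that a Visit 1 check could prevent in a patient who already has the condition then, and only if the check detects it and nothing else does first. Neither the detection probability nor the rate of such conditions is in the documents, so no expected benefit can be calculated.

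**The case against.** The strongest reply is that the protocol already has the means to deal with this. A pregnancy found at any visit requires withdrawal, so for a known pregnancy the rewording mainly moves a mandatory removal forward to entry. The 7.1 interview is compulsory and takes place at the time of entry, and with the 10.1 review it would probably catch most other known conditions. Criterion 8 requires continued agreement to contraception. Section 11.4 places the drug in Pregnancy Category B; the appended package insert reports no embryofetal effects in mice and rabbits, though it does report lower pup weight and survival in rats. The Week 2 call asks about adverse events. Even same-day patients start before their lead-in laboratory results are known (10.1), so the plan accepts some checking after entry. All of this stands and keeps the point small. It does not supply a rule for the gap, and withdrawal cannot act on a pregnancy that an omitted test has not revealed.

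On the C-SSRS, the waiver can be read as a specific exception to a general rule. That is a fair reading, but the protocol does not say so, and 10.3.1.1 and 10.3.1.2 make no exception.

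Three stronger readings are tempting, and the documents do not support them.

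- A reader might infer that the withdrawal rule for ideation scores of 4 or 5 would miss a score found at a delayed Visit 1. That rule is worded "on the Suicidal Ideation section of the C-SSRS at a clinic visit following enrollment, the patient should be withdrawn from the study", and the synopsis describes the baseline as measured "prior to enrollment into the P303 extension study". But the synopsis phrase describes the measurement from the final lead-in visit, not a new C-SSRS at a later Visit 1, so the inference is weak.
- A reader might take the 10.2 note on using lead-in results as a waiver of safety checks. It sits under efficacy assessments and is doubtful support for that.
- A reader might infer that adverse event counts are distorted. SAP 10.1 counts as newly emergent only events that start after the first P303 dose or lead-in events that worsen, so a new event starting in the gap is not counted as newly emergent.

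**Conclusion.** The point holds as a gap in the written entry rules, with a narrow safety consequence. Criterion 4 does not reach the interval between the lead-in study and Visit 1. For gaps of 1 to 14 days the waiver lets drug start on an earlier pregnancy test, with the next scheduled one 22 to 49 days after it. The C-SSRS instructions for the same visit do not agree.

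A reader might go further and infer that patients with known new conditions would be enrolled freely, or that the dose counts measure harm avoided. The first overlooks the interview, the review and mandatory withdrawal for pregnancy. The second treats a ceiling for affected patients as an average over delayed patients.

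The intervals rest only on the protocol's visit windows and on the lead-in results being carried forward. The size of the safety gain is unknown but likely small: a delay is expected only in extenuating circumstances, and the share of patients affected is not stated. No endpoint or planned analysis is shown to be affected. The change is worth making because it is cheap and turns a stated intention into a rule.

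**What to change.** 1. In 7.2 and the synopsis, open criterion 4 with: 'From entry into the lead-in study through P303 Visit 1 (before dispensing), the patient has had no…'. Ending the period before dispensing matters, because the first dose is taken at bedtime after the visit and the site cannot verify anything later when it decides eligibility.
2. In 9.1.4 and Appendix 1 footnote a, state that whenever Visit 1 is not on the same day as the final lead-in visit, the since-last-visit C-SSRS and, for women of child-bearing potential, a urine pregnancy test are done at Visit 1 before dispensing. Drug is not dispensed if the test is positive or ideation is scored 4 or 5. This also settles the conflict with 10.3.1.1 and 10.3.1.2.
3. Keep the 14-day carry-over for everything else, including the BDI-II and the central laboratory tests. The two checks chosen are those whose results already call for withdrawal under the protocol; worsening depression would be covered by the reworded criterion and the interview.

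The cost is one phrase in a criterion, a short addition to 9.1.4 and the footnote, and, for the few delayed patients, one short interview and (where applicable) one dipstick at a visit they attend anyway. Same-day entries are unaffected. A very early pregnancy or undisclosed ideation could still be missed.
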